6.5.3 Death

All deaths and causes of death will be summarized by treatment arm, including those occurred during the study treatment period and those reported during the survival follow-up period after treatment completion/discontinuation. Patient data listings of death will be provided.

6.5.4 Laboratory Values

Laboratory safety tests of serum chemistry and hematology will be evaluated for selected parameters described in Table 3. The actual value and the change from baseline to each post-baseline visit and to the end of treatment will be summarized by visit using descriptive summary statistics (n, mean, standard deviation, median, minimum, maximum for continuous variables).

Urinalysis includes blood, protein, ketones, glucose, red blood cells, and white blood cells. Urinalysis results will not be summarized descriptively by visit.

Laboratory parameters that are graded in NCI CTCAE (v.4.03) will be summarized by shifts from baseline CTCAE grades to maximum post-baseline grades. In the summary of laboratory parameters by CTCAE grade, parameters with CTCAE grading in both high and low directions

will be summarized separately. Number (percentage) of patients with abnormal postbaseline laboratory values will be summarized.

Patient data listings of selected hematology and serum chemistry parameters, and urinalysis will be provided.

A summary of the liver function test abnormalities will also be presented based on Hy's law laboratory criteria defined as 1) Alanine aminotransferase (ALT) or Aspartate aminotransferase (AST) > 3 x ULN, 2) Total bilirubin (TBL) > 2 x ULN and 3) Alkaline phosphatase (ALP) < 2 x ULN and ALP ≥ 2 x ULN for patients with 1) and 2), at any postbaseline visit.

Table 3. Serum Chemistry, Hematology, and Urinalysis Laboratory Tests

Serum Chemistry	Hematology	Urinalysis
Alkaline phosphatase (ALP)	Hemoglobin	Blood
Alanine aminotransferase (ALT)	Platelet counts	Protein
Aspartate aminotransferase (AST)	White blood cell (WBC) count	Ketones
Albumin	Neutrophil	Glucose
Total bilirubin	Lymphocyte	Red blood cells
Blood Urea Nitrogen		White blood cells
Creatinine		
Chloride		
Phosphate		
Glucose		
Lactate dehydrogenase		
Total Protein		
Potassium		
Sodium		

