5.6. Follow-Up Phase

5.6.1. Safety Follow-up

All patients who permanently discontinue study drug and have not initiated new anticancer therapy will be followed for AEs and serious AEs (SAEs) as outlined in Section 9.3.1. Approximately 30 days after the last day of study drug or before initiation of new anticancer therapy, whichever occurs first, a safety follow-up will occur with the safety assessments outlined in [Appendix 1](#). If new anticancer therapy is inadvertently initiated before this safety follow-up (eg, without the knowledge of the study center team), a safety follow-up should be scheduled as soon as possible.

For patients who do not want to or cannot return to the clinic for the safety follow-up, the patient should be contacted by telephone for a review of AEs. If these attempts of contact are unsuccessful, the additional attempts detailed in Section 5.6.3 should be made.

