- b. Patients must initiate study treatment within 4 days after randomization. Administration of BGB-290 or placebo will continue until PD, as assessed by investigator per RECIST Version 1.1, unacceptable toxicity, death, or another discontinuation criterion is met (Sections 5.5 and 5.7). A cycle is 28 days. Assessments shown for Cycle 3 apply to all subsequent cycles except for required tumor assessments that occur every 8 weeks ± 7 days (every second cycle) and blood collection for biomarkers occurs only on Day 1 of Cycle 4 (not any other Day 1 of \geq Cycle 3).
- c. Unscheduled visits may occur any time as necessary as per investigator decision or patient's request for reasons such as assessment or follow-up of AEs. Study activities, as indicated by 'X,' should be performed based on the reason for the unscheduled visit. If PD is suspected, imaging studies should be performed and blood for biomarkers should be obtained as appropriate.
- d. The EOT visit should occur within 7 days after BGB-290 or placebo has been permanently discontinued. A visit should be scheduled as soon as possible, but the EOT visit may occur later after discussion with the medical monitor for specific circumstances, such as prolonged hospitalization. The visit at which tumor assessments showed PD may be used as the EOT visit providing all required assessments were performed. Tumor assessments do not have to be repeated if they were performed within 14 days of the EOT visit or at a prior response evaluation that documented PD. An ECG does not have to be repeated if it was performed within 14 days of the EOT visit.
- e. Approximately 30 days after the last day of study drug or before initiation of new anticancer therapy, whichever occurs first, a safety follow-up will occur with the outlined safety assessments. If new anticancer therapy is initiated before this safety follow-up, a safety follow-up should be scheduled as soon as possible. For patients who do not want to or cannot return to the clinic for the safety follow-up, the patient should be contacted by telephone for a review of AEs. If these attempts of contact are unsuccessful, the additional attempts detailed in Section 5.6.3 should be made.

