6.2 DATA ANALYSIS GENERAL CONSIDERATIONS

6.2.1 Definitions and Computations

Study day: Study day will be calculated in reference to the randomization date for efficacy analysis, and date of the first dose of study treatment for safety analysis. For assessments conducted on or after the randomization date or date of the first dose of study treatment, study day will be calculated as (assessment date – randomization date or date of first dose of study treatment + 1). For assessments conducted before the randomization date or date of the first dose of study treatment, study day is calculated as (assessment date – randomization date or date of first dose of study treatment). There is no study day 0.

In the situation where the event date is partial or missing, the date will appear partial or missing in the listings. Study day and any corresponding durations will be presented based on the imputations specified in Appendix 10.1.

Treatment duration: The treatment duration will be calculated as (date of last dose of study treatment – date of first dose of study treatment + 1).

Baseline: Unless otherwise specified, a baseline value is defined as the last non-missing value collected before the time of first dose date. The baseline tumor assessment is defined as the screening assessment in reference to randomization date.

All calculations and analyses will be conducted using SAS version 9.4 or higher.

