6.5.2 Adverse Events

AEs will be graded by the investigators using NCI CTCAE v4.03. The AE verbatim descriptions (investigator terms from the CRF) will be classified into standardized medical terminology using the Medical Dictionary for Regulatory Activities (MedDRA). Adverse events will be coded to the MedDRA (Version 22.0 or higher) lower level term closest to the verbatim term. The linked MedDRA preferred term (PT) and primary system organ class (SOC) are also captured in the database.

A treatment-emergent adverse event (TEAE) is defined as an AE that had an onset date on or after the date of the first dose of study treatment through 30 days after the last dose (permanent discontinuation of study treatment) or initiation of new anticancer therapy. Only those AEs that were treatment emergent will be included in summary tables. All AEs, treatment emergent or otherwise, will be presented in patient data listings.

An overview table of patients with at least one TEAE will be presented, as the number (percentage), with the incidence of following:

- patients with any TEAE
- patients with any TEAE with Grade 3 or higher
- patients with any serious TEAE
- patients with any TEAE leading to death
- patients with any TEAE leading to treatment discontinuation
- patients with any TEAE leading to dose modification
 - patients with any TEAE leading to dose interruption
 - patients with any TEAE leading to dose reduction
- patients with any treatment-related TEAE
- patients with any treatment-related TEAE with Grade 3 or higher
- patients with any treatment-related serious TEAE

- patients with any treatment-related TEAE leading to death
- patients with any treatment-related TEAE leading to treatment discontinuation
- patients with any treatment-related TEAE leading to dose modification
 - patients with any treatment-related TEAE leading to dose interruption
 - patients with any treatment-related TEAE leading to dose reduction

Summaries of all above TEAEs will also be reported as the number (percentage) of patients by SOC and PT.

Summaries of all TEAEs, SAE, Grade 3 or higher TEAEs, treatment-related TEAEs, and TEAE leading to treatment discontinuation will also be provided by PT only in descending order of frequency.

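### SAP 6.5.4 sets no end to the window for the worst-grade, abnormal-value and Hy's law laboratory summaries, so a blood sample taken after a switch to new anticancer therapy can be attributed to study drug or placebo

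*SAP*

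**What the plan says.** SAP 6.5.4 defines three patient-level laboratory summaries, none with an upper time limit:

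- CTCAE-graded parameters "will be summarized by shifts from baseline CTCAE grades to maximum post-baseline grades".
- The number and percentage of "patients with abnormal postbaseline laboratory values will be summarized".
- The Hy's law table, which splits by alkaline phosphatase "for patients with 1) and 2), at any postbaseline visit".

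The only boundary elsewhere in the SAP is the lower one. Section 6.2.1 states that "a baseline value is defined as the last non-missing value collected before the time of first dose date". No on-treatment or treatment-emergent period is defined for laboratory data.

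Adverse events are treated differently. SAP 6.5.2 counts those with onset from first dose "through 30 days after the last dose (permanent discontinuation of study treatment) or initiation of new anticancer therapy". Protocol 10.6.2 makes clear that the earlier of the two dates applies. SAP 6.3.7 uses similar limits for concomitant medications.

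On sampling, Protocol 5.6.1 and Appendix 1 (footnote e) place the safety follow-up about 30 days after the last dose, or before new anticancer therapy if that is sooner. Both then cover the case where therapy has already begun. Footnote e reads "If new anticancer therapy is initiated before this safety follow-up, a safety follow-up should be scheduled as soon as possible". Section 5.6.1 is narrower: "If new anticancer therapy is inadvertently initiated before this safety follow-up (eg, without the knowledge of the study center team". The Appendix 1 grid marks hematology and chemistry at the unscheduled, end-of-treatment and safety follow-up visits, but not in long-term follow-up.

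**The concern.** A worst-grade summary depends on each patient's single most extreme value. If that value was drawn after the next treatment started, it replaces everything observed on study drug or placebo. Protocol 1.1 lists irinotecan, docetaxel and paclitaxel among the second-line options, and Protocol 1.4.2.3 names hematologic events as being of interest for BGB-290. A cytopenia caused by the next therapy would therefore land in the tables that matter most for this drug. For Hy's law the sensitivity is greater, because one case attracts attention by itself.

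Protocol 9.1.5 makes a laboratory abnormality an adverse event only when the investigator judges it clinically significant or it meets similar conditions. The graded laboratory tables are thus the systematic record of cytopenia and liver abnormality, and it should be clear which treatment period they describe. As written, a programmer following SAP 6.5.4 would include values taken after a switch.

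**Working it through.** **Step 1: compare the windows.**

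| Summary | Start | End |
|---|---|---|
| Adverse events (SAP 6.5.2, Protocol 10.6.2) | first dose | last dose + 30 days, or new anticancer therapy if earlier |
| Laboratory shift to worst grade (SAP 6.5.4) | after baseline | none stated |
| Abnormal laboratory values (SAP 6.5.4) | after baseline | none stated |
| Hy's law (SAP 6.5.4) | after baseline | none stated |

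**Step 2: find which samples can fall after a switch.**

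- Safety follow-up: by default before new therapy; afterwards only under the fallback in Protocol 5.6.1 and Appendix 1 footnote e. Bloods are marked at this visit.
- End-of-treatment visit: starting new anticancer therapy is itself a listed reason for stopping study drug (Protocol 5.5.1). The visit is due within 7 days of stopping and may be later in specific circumstances (Protocol 5.5.2). Bloods are marked.
- Unscheduled visits: possible at any time, with bloods as needed.
- Long-term follow-up: no hematology or chemistry scheduled.

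So the exposure is real but narrow.

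**Step 3: scale.** The documents give no figure for post-switch samples. One patient in an arm of 64 is 1/64 = 1.6 percentage points.

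For a rough range I use the design assumptions in SAP 5: placebo median PFS 6.0 months, HR 0.63, accrual 20 months, duration 26 months. As a check on those inputs, the Schoenfeld formula gives 4 × (1.2816 + 0.8416)² / (ln 0.63)² = 84.5, rounded up to 85, which matches the plan. The point itself does not depend on this figure.

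With exponential PFS, uniform accrual and no dropout, the probability of a PFS event by cutoff is p = 1 − [exp(−λ(T−A)) − exp(−λT)] / (λA), where λ = ln 2 / median, A = 20 and T = 26.

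- Placebo, median 6.0: p = 0.805, so 64 × 0.805 = 51.5 patients.
- BGB-290, median 6.0/0.63 = 9.52: p = 0.660, so 64 × 0.660 = 42.2 patients.

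These sum to 93.7, above the planned 85 events, so the range below is slightly generous.

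Assumptions not in the documents: a share f of 5% to 30% of patients with a PFS event have bloods after new therapy starts, and a share q of 10% to 30% of those draws set a new worst grade. Patients added per arm = 64 × p × f × q.

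| | Placebo | BGB-290 | Net, same f and q in both arms |
|---|---|---|---|
| f = 5%, q = 10% | 0.26 (0.4 points) | 0.21 (0.3 points) | 0.05 patients (0.1 points) |
| f = 30%, q = 30% | 4.64 (7.2 points) | 3.80 (5.9 points) | 0.84 patients (1.3 points) |

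**Step 4: direction.** The net leans toward placebo only because f was set equal in both arms. It reverses once f on BGB-290 exceeds f on placebo by a factor of 51.5/42.2 = 1.22. For example, with q = 20%, f = 10% on placebo adds 1.6 points while f = 20% on BGB-290 adds 2.6 points.

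**The case against.** The strongest answer is that the protocol already controls this. The default is to draw the safety-visit bloods before the switch, and Protocol 5.6.1 describes the exception as inadvertent. That stands: these samples are exceptional. It does not close the gap, because footnote e states the same fallback without that qualifier, and no sentence in the SAP excludes the values once collected.

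Second, the tables are descriptive, with no test or decision rule attached. By-visit summaries and listings of hematology and chemistry are already planned, and adverse event incidence and severity already have a bounded window. This also stands, and it limits the importance of the point.

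Third, laboratory and adverse event tables differ by design, because of the clinical-significance test in Protocol 9.1.5. Correct: matching the windows would not make the tables agree, and disagreement alone is not the defect. The defect is attribution to the wrong treatment period.

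A reader might infer something stronger: that next-therapy toxicity is routinely counted, that it inflates placebo cytopenia by several points because placebo patients progress sooner, and that drug toxicity is thereby hidden. The documents do not support this. They give no rate of post-switch sampling and no switch timing by arm. A placebo-only figure is not the between-arm effect. Patients who stop BGB-290 for toxicity and then switch would add contamination to the drug arm. The Phase 1 rates of related Grade 3 neutropenia (7%) and anemia (11%) in Protocol 1.4.2.3 are drug-related adverse events in 45 patients, so they are not a direct yardstick for graded laboratory values.

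**Conclusion.** The point holds in limited form. Followed as written, SAP 6.5.4 attributes some values taken on the next therapy to BGB-290 or placebo, in the exceptional patients sampled after a switch. The firm harm is misattribution within an arm, at 1.6 points per affected patient, and the possibility of a Hy's law case that belongs to another drug.

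The net between-arm effect is probably small: under one patient per arm across the range worked above. That range rests on assumed sampling and worst-grade rates, equal in both arms, for which the documents offer no evidence. The direction is not established. No efficacy analysis is affected. This is a minor improvement to descriptive safety tables, justified mainly by how little it costs.

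**What to change.** In SAP 6.5.4, limit the shift, worst-grade, abnormal-value and Hy's law summaries to values from first dose through the safety follow-up (about 30 days after the last dose) or the start of new anticancer therapy, whichever comes first. Two details need stating:

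- **A visit allowance.** The safety follow-up is due at approximately 30 days. A hard cut at day 30 would discard compliant samples from patients who had no new therapy, and with them any delayed effect of study drug.
- **Same-day samples.** Count a sample drawn on the day new therapy starts if it was taken before that therapy, and state the default where the order is not recorded.

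Keep later values in the listings with a flag. The cost is one sentence and one date filter. Subsequent therapy dates are already collected (Protocol Appendix 1, footnote o), and SAP Appendix 10.1 already has rules for incomplete ones. The downside is that a few late values leave the summary tables.

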6.5.5 Vital Signs

Descriptive statistics for vital sign parameters (systolic and diastolic blood pressure, pulse rate, temperature, and weight) and changes from baseline will be presented by visit. Vital signs will be listed by patients and visits.

6.5.6 Electrocardiograms (ECG)

ECG will be obtained during screening, predose and 2 hours postdose on Cycle 1 Day 1 and Cycle 1 Day 15, and end of treatment (EOT). Additional ECGs may be performed as clinically

indicated at other timepoints. ECG findings at baseline and all other predose and postdose assessments on the first cycle and EOT will be descriptively summarized.

The number and percentage of patients satisfying the following QTcF conditions at any time post-baseline will be summarized:

- 450, > 480, or > 500 msec
- ≤ 30 msec increase from baseline, > 30 and ≤ 60 msec increase from baseline, or > 60 msec increase from baseline

Patient listing of ECG will be provided for all ECG recordings with the indicator whether the abnormality is clinical significance. For patients without QTcF, all measures in QTcB will be transformed into QTcF by standard derivation method in summary tables.

6.5.7 Eastern Cooperative Oncology Group (ECOG)

ECOG scores will be summarized by visit using descriptive statistics for Safety Analysis Set.

6.6 PHARMACOKINETIC ANALYSES

Individual and summary plasma concentration of pamiparib will be presented.

PLASMA CONCENTRATIONS

PK samples will be collected from patients at predose (within 30 minutes before dose) and 2 hours (± 30 minutes) postdose on Cycle 1 Day 1 and Cycle 1 Day 15. PK sampling will be collected only at sites that have the capability to collect PK samples. Details concerning collection, handling, and processing of the PK plasma samples will be provided in the study manual. PK samples collected from patients assigned to placebo treatment will not be analyzed for pamiparib concentrations.

Plasma pamiparib concentration-time data will be summarized in tabular form. Pharmacokinetic concentration data for pamiparib will be listed including the dose level, relative time to dosing, actual sample collection time. The concentration data will also be summarized with descriptive statistics for each timepoint. The number of patients with non-missing plasma concentration, mean, standard deviation, minimum, median, maximum, geometric coefficient of variation and geometric mean will be included in the summary.

6.7 PHARMACODYNAMIC ANALYSES

Correlative biomarker analyses in tumor tissues and blood will be performed. A separate statistical analysis plan will outline details of the biomarker analyses.

7 INTERIM ANALYSIS

No interim analysis is considered in this study.

8 CHANGES IN THE PLANNED ANALYSIS

- The Per-Protocol (PP) analysis set defined in the protocol BGB-290-303 (version 1.0, 2020-02-13) will not be considered in the analysis.
- Progression-free survival 2 (PFS2) by investigator assessment as secondary efficacy endpoints defined in the protocol BGB-290-303 (version 1.0, 2020-02-13) will not be considered in the analysis.
- Confirmation of response will not be required for ORR in randomized clinical studies per RECIST v1.1. No confirmation of response required for the analysis of DOR and Time to response to be consistent with analysis of ORR.
- The stratification factor of HRD status (LOH_{high} versus LOH_{low} versus unknown) will not be included as strata for PFS, OS, and TSST nor covariate in primary or secondary analyses due to high rate of patients with unknown LOH reported. And the Region will have three strata (China/Hong Kong/Taiwan versus Australia/Europe/North America versus Japan/South Korea/rest of world [ROW]) for PFS, OS, TSST, and covariate in primary or secondary analyses after combining patients in Japan/South Korea with patients in ROW as small number of patients were enrolled in Japan and no patients were enrolled in South Korea.
- No PK parameters will be derived and reported in clinical study report. The definition of PK analysis set is thus modified as all patients who have at least one plasma concentration.

9 REFERENCES

- Clopper, C. and Pearson, ES. The use of confidence or fiducial limits illustrated in the case of the binomial, *Biometrika* 1934;26: 404-413.
- Collett D. *Modelling survival data in medical research*. New York: Chapman & Hall; 1994.
- Common Terminology Criteria for Adverse Events (CTCAE). Version 4.0. United States Department of Health and Human Services, National Institutes of Health, National Cancer Institute, Washington, DC, USA, May 28, 2009.
- Greenwood M. "The natural duration of cancer". *Reports on Public Health and Medical Patients* (London: Her Majesty's Stationery Office). 1926; 33:1-26.

10 APPENDIX**10.1 HANDLING OF PARTIALLY MISSING DATES****1) Adverse Events**

The imputation rule for the safety analyses will be used to address the issues with partial dates. When the start date or end date of an adverse event is partially missing, the date will be imputed to determine whether the adverse event is treatment-emergent. When in doubt, the adverse event will be considered treatment emergent by default. The following rules will be applied to impute missing or partial dates for adverse events:

	Missing	Impute	Exception
Start Date	Day	01	If Month and Year = Month and Year of treatment start date, then set to treatment start date
	Day/Month	January 01	If Year = Year of treatment start date, then set to treatment start date
	Day/Month/Year or Year only	Do not impute	N/A
End Date	Day	Last day of the month	N/A
	Day/Month	December 31	N/A
	Day/Month/Year or Year only	Do not impute	N/A

If the imputed AE start date becomes after AE end date, then update AE start date same as AE end date. And if the imputed start date or end date becomes after death date, then set to death date.

The following rule will be applied to impute missing toxicity grade of AE:

1. The highest grade will be used from patient's AEs with the same preferred term.
2. If patient has no AEs with the same preferred terms, the highest grade of the AEs with the same SOC will be used.
3. If patient has no same SOC, the highest grade of all AEs from that patient will be used.

4. If it is the single AE reported for that patient, no imputation for the missing grade will be done.

2) Prior/Concomitant Medications, Disease and Medical History, Prior Therapy (Drug, Surgery/Procedure, Radiotherapy)

	Missing	Impute	Exception
Start Date	Day	01	N/A
	Day/Month	January 01	N/A
	Day/Month/Year or Year only	Do not impute	N/A
End Date	Day	Last day of the month	N/A
	Day/Month	December 31	N/A
	Day/Month/Year or Year only	Do not impute	N/A

For concomitant medications; if the imputed start date or end date becomes after death date, then set to death date.

For disease history and prior therapy, including initial diagnosis date, relapse date, therapy date (start/end date), or surgery date; if the imputed start date or end date becomes after first dose date, then set to first dose date - 15.

3) Initial Diagnosis, Metastatic Disease, and Most Recent Progression

	Missing	Impute	Exception
Initial Diagnosis Date/ Metastatic Disease Date/ Most Recent Progression Date	Day	01	N/A
	Day / Month	January 01	N/A
	Day / Month / Year or Year only	Do not impute	N/A

If the imputed initial diagnosis date, metastatic disease date or most recent progression date is on or after the treatment start date, then set to treatment start date - 1.

4) Death

In case complete death dates are not recorded, impute as follows:

[figure not shown]
- If both month and day are missing, then the imputed month and day will be 01Jan or the last date of patient known to be alive + 1, whichever is later.
- If only day is missing, the death will be assumed to be on the first day of the month or the last date of patient known to be alive +1, whichever is later.

5) New Anticancer Therapy

If the start day of a subsequent anticancer therapy is incomplete or missing, impute as follows:

- If both month and day are missing,
 - 1) impute the date as 31Dec, if the year is earlier than the year of the first PD date + 1 or the treatment end date + 1, whichever is later.
 - 2) impute the date as 01Jan, if the year is later than the year of the first PD date or the treatment end date + 1, whichever is later.
 - 3) impute the date as the first PD date + 1 or the treatment end date + 1, whichever is later, if the year is the same year of first PD date + 1 or the treatment end date + 1, whichever is later.
- If only day is missing,
 - 1) impute the date as the first day of the month if year and month are available and partial new anticancer therapy date still could indicate it is at least one month later than the first PD date +1 or the treatment end date +1, whichever is later.
 - 2) impute the date as the last day of the month if year and month are available and partial new anticancer therapy date still could indicate it is at least one month earlier than the first PD date +1 or the treatment end date +1, whichever is later.
 - 3) impute the date as the first PD date +1 or the treatment end date +1, whichever is later, if the year and month are the same year and month of first PD date +1 or the treatment end date +1, whichever is later.

Signature Page for VV-CLIN-033243 v1.0

Approval	 Biometrics 28-Aug-2020 22:30:20 GMT+0000
----------	--

Approval	 Biometrics 31-Aug-2020 03:26:54 GMT+0000
----------	--

Approval	 Clinical Development 02-Sep-2020 14:48:54 GMT+0000
----------	---

Approval	 Clinical Development 08-Sep-2020 17:45:28 GMT+0000
----------	---

Signature Page for VV-CLIN-033243 v1.0

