9.1.2. Assessment of Severity

The investigator will make an assessment of severity for each AE and SAE reported during the study. AEs and SAEs should be assessed and graded based upon the NCI-CTCAE Version 4.03.

Toxicities that are not specified in the NCI-CTCAE will be defined as follows:

- Grade 1: Mild; asymptomatic or mild symptoms; clinical or diagnostic observations only; intervention not indicated
- Grade 2: Moderate; minimal, local, or noninvasive intervention indicated; limiting age-appropriate instrumental activities of daily living
- Grade 3: Severe or medically significant but not immediately life-threatening; hospitalization or prolongation of hospitalization indicated; disabling; limiting self-care activities of daily living
- Grade 4: Life-threatening consequences; urgent intervention indicated
- Grade 5: Death related to AE

Note: The terms “severe” and “serious” are not synonymous. Severity is a measure of intensity (eg, grade of a specific AE, mild [Grade 1], moderate [Grade 2], severe [Grade 3], or life-threatening [Grade 4]); whereas, seriousness is classified by the criteria based on the regulatory definitions. Seriousness serves as the guide for defining regulatory reporting obligations from the sponsor to applicable regulatory authorities as described in Section 9.2.

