4.2 SECONDARY ENDPOINTS

Efficacy assessment:

- OS, defined as the time from randomization to death due to any cause
- Time to second subsequent treatment (TSST), defined as the time from randomization until the second subsequent anticancer therapy or death after next-line therapy
- ORR, defined as the proportion of patients with a best overall response of CR or PR per RECIST Version 1.1 by investigator assessment
- DOR, defined as the time from the first documented confirmed response of CR or PR to PD per RECIST Version 1.1 by investigator assessment or death due to any cause, whichever occurs first
- Time to response, defined as the time from randomization to the first documented response of CR or PR per RECIST Version 1.1 by investigator assessment

Safety assessment:

- Incidence, timing, and severity of TEAEs, graded according to NCI-CTCAE Version 4.03 or higher
- Safety and tolerability assessment of laboratory measurements, vital signs, and ECG findings

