All TEAEs, SAE, Grade 3 or higher TEAEs, treatment-related TEAEs and TEAEs leading to treatment discontinuation will also be summarized by SOC, PT, and maximum severity. A patient will be counted only once by the highest severity grade according to CTCAE v.4.03 within an SOC and PT, even if the patient experienced more than 1 TEAE within a specific SOC and PT.

Patient data listings of all AEs, SAEs, treatment-related AEs, Grade 3 or above AEs, AEs that led to death, AEs that led to treatment discontinuation, and AEs that led to dose modification will be provided.

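### The SAP's rule for a missing adverse event grade has no cap below Grade 5 and no treatment-emergent limit on the source event, so a non-fatal event can be tabulated as Grade 5

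*SAP*

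**What the plan says.** SAP section 6.2.2 leaves missing safety data unimputed unless the SAP says otherwise. Appendix 10.1, part 1 (Adverse Events), does say otherwise for toxicity grade, in four ordered steps:

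- Step 1: "The highest grade will be used from patient's AEs with the same preferred term".
- Step 2, when there is no event with that preferred term: "the highest grade of the AEs with the same SOC will be used".
- Step 3: "If patient has no same SOC, the highest grade of all AEs from that patient will be used".
- Step 4: "If it is the single AE reported for that patient, no imputation for the missing grade will be done".

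Protocol section 9.1.2 gives the meaning of the top grade, in its scale for toxicities that NCI-CTCAE does not list: "Grade 5: Death related to AE".

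SAP section 4.2 makes severity a secondary safety endpoint: "Incidence, timing, and severity of TEAEs, graded according to NCI-CTCAE Version 4.03 or higher". Section 6.5.2 uses the grades in two ways. One is counts such as "patients with any TEAE with Grade 3 or higher", with a treatment-related counterpart. The other is the set of tables showing each patient's worst grade: "A patient will be counted only once by the highest severity grade according to CTCAE v.4.03 within an SOC and PT". Nothing in 6.5.2 excludes or marks an imputed grade.

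**The concern.** Grades 1 to 4 describe how severe an event was. Grade 5 states how it ended. Carrying a Grade 3 from one event to another is a pessimistic guess about an unknown. Carrying a Grade 5 asserts a death from an event that may be recorded as resolved. Because relatedness stays with the ungraded event while the grade comes from elsewhere, the rule can also show a treatment-related Grade 5 in a patient with no related fatal event.

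The source pool is a second gap. Step 3 draws on all of the patient's AEs. Under protocol section 9.3.1, SAEs are collected from consent, before first dose, and related SAEs are still reported after the 30-day window. Section 9.4.6 asks for MDS and AML whenever they occur. A grade from outside the treatment-emergent period can therefore become the grade of a TEAE.

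At stake is the accuracy of the severity tables, where Grade 5 entries are likely to be few and each one will be read closely.

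**Working it through.** The plan states no figure for this rule, so there is none to reproduce. The check is to apply the four steps literally to constructed patients and compare the section 6.5.2 row maxima before and after imputation. The patients are illustrations, not trial data. In each, the ungraded event is non-fatal, on treatment and judged related, and the graded event shown is the patient's only other AE.

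| Graded event | Ungraded event | Step | Grade assigned | What changes |
|---|---|---|---|---|
| Pneumonia, Grade 5, unrelated | Nausea | 3 | 5 | Nausea PT, GI SOC and treatment-related maxima go from none to 5 |
| GI haemorrhage, Grade 5, unrelated | Nausea | 2 | 5 | Nausea PT and treatment-related maxima go from none to 5; GI SOC stays 5 |
| Haemorrhage, Grade 5, unrelated | Second haemorrhage | 1 | 5 | PT and SOC maxima stay 5; treatment-related goes from none to 5 |
| Anaemia, Grade 3, related | Alopecia | 3 | 3 | Alopecia PT and skin SOC go from none to 3; patient-level maxima stay 3 |
| Sepsis, Grade 4, SAE before first dose | Nausea | 3 | 4 | Patient's maximum TEAE grade goes from none to 4, so the patient newly counts as Grade 3 or higher |
| None | Nausea | 4 | Missing | Nothing |

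Four things follow.

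1. The missing cap matters in steps 1 to 3, not only in the last. In step 1 with a treatment-emergent source, the all-cause PT and SOC maxima cannot move, but the treatment-related row can.
2. The first row depends on its conditions. If the patient had another graded nausea or another graded GI event, step 1 or step 2 would supply the grade and the pneumonia would not be used.
3. When the source is itself a TEAE, the number of patients with any Grade 3 or higher TEAE is unchanged, because that patient already counts. The number changes only with a source outside the treatment-emergent period, as in the sepsis row. The treatment-related count can change when the source is unrelated.
4. Scale: SAP section 5 plans about 64 patients per arm. One affected patient moves a row by 1/64 = 1.56 percentage points, and two by 2/64 = 3.12. These are the sizes of hypothetical cases; they do not estimate how many will occur.

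**The case against.** The strongest defence is that worst-case filling is a deliberate, conservative choice. The same appendix treats an AE as treatment-emergent when in doubt. The rule looks first to the same PT and then to the same SOC, and reaches for any AE only as a last resort. This stands for Grades 3 and 4. A reader might infer that steps 2 and 3 are wrong altogether because they can raise a mild event to Grade 3. The documents do not support that: removing those steps could understate Grade 3 or higher events, so the choice is a trade-off. The defence does not reach Grade 5 for an event recorded as non-fatal, since there is then no doubt to resolve conservatively.

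The opportunity is also limited. Protocol section 9.1.2 has the investigator grade every AE, section 8.2 provides for validation queries and completeness review, and SAP section 6.2.6 calls for complete, reviewed data before analysis. Under protocol section 9.4.4, deaths solely due to progression are not reported as SAEs, which reduces the number of Grade 5 sources. All of this stands and keeps the point minor.

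The cited Grade 5 definition belongs to the scale for toxicities outside NCI-CTCAE. That is a fair limit on the citation, but it is the meaning the protocol itself attaches to the grade, and nothing in either document gives another.

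**Conclusion.** The rule is wrong as written on one narrow matter: it allows Grade 5 to be imputed to an event that was not fatal. It has a related gap in not limiting sources to treatment-emergent events. The consequences fall mainly on the PT, SOC and treatment-related grade rows. The overall Grade 3 or higher count is affected only through a source outside the treatment-emergent period. Few cases are expected, but that is a judgement from the data-quality provisions, because no missing-grade rate is given. The conclusion assumes that the rule is programmed as it reads and that imputed grades enter the section 6.5.2 tables.

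Two stronger conclusions should not be drawn:

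- A reader might infer that the number of deaths would be inflated. TEAEs leading to death are a separate category in section 6.5.2, and deaths and their causes have their own summary in section 6.5.3. Neither is said to be derived from grade. If they come from recorded outcome, the result is a disagreement between tables, not a wrong death count.
- A reader might infer a bias between pamiparib and placebo. That would depend on the number of missing grades and of severe events in each arm. Neither is known, and no direction or size can be given.

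The PFS analysis does not use AE grades and is not affected.

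**What to change.** Keep the conservative hierarchy in Appendix 10.1 and add three conditions:

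- In every imputation step, cap the imputed grade at 4 unless the ungraded event's own recorded outcome is fatal.
- For the TEAE tables, take the source grade only from treatment-emergent events. If there is none, leave the grade missing, as step 4 already does for a sole AE.
- Flag imputed grades in the AE listings.

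In the cases above, the three Grade 5 assignments become Grade 4, the alopecia stays at Grade 3, and the nausea after the pre-treatment sepsis stays ungraded. The first three remain pessimistic, in keeping with the intent of the rule, but no longer report a death.

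The cost is a few lines of SAP text and one or two extra programming conditions. An occasional event may also remain ungraded in the TEAE tables.
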